3.2 Dose allocation

The trial design ensures no treatment schedule skipping and the treatment schedule assigned will be that estimated to be closest to but not above the target toxicity level (TTL). However, if the lowest schedule is estimated to be above the TTL we will keep assigning the lowest schedule until we are certain it is too toxic, at which point the trial may start again using a lower dose of drug. When escalating, the treatment schedule can only increment by one level if escalating to an untried schedule, but there will be no restriction on treatment schedule de-escalation. Each escalation decision will be made by the TMG based on the recommendation from the TiTE-CRM model and the accumulated experience of the recommended schedule. Full details of each dose decision are found in the Protocol Decision Point Plan (V1.0, 28Jun2019) but briefly: TMG to review the dose selected by the statistical model on the basis of the accumulated data and either:

- Confirm the selected dose **or**
- Over-rule the selected dose and choose an alternative dose for the next participant & may convene a meeting of the Safety Review Committee (SRC) **or**
- Agree to convene a meeting of the Safety Review Committee (SRC) for further input as the TMG is unable to reach a decision **or**

Agree that a protocol defined stopping rule has been met and that the trial should be stopped.

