2 TRIAL DESIGN

This will be a single arm, open-label, phase I dose escalation trial using the Time-To-Event Continual Reassessment Method (TiTE-CRM) to find the optimal treatment schedule. The TiTE-CRM method uses critical toxicity summaries of accumulated patient data from all participants treated with at least one dose of the IMP within the corresponding trial stage and for whom up-to-date data has been provided (trial unit will endeavour to ensure contemporaneous data is received for all participants) and it is not necessary for a patient to complete the full observation period before consenting the next patient. This results in a better estimation of the MTD and shorter study duration respectively and is particularly useful in trials involving radiotherapy where the toxicity follow-up phase is longer.

The trial design ensures no treatment schedule skipping and the treatment schedule assigned will be that estimated to be closest to but not above the MTD. However, if the lowest schedule is estimated to be above the MTD we will keep assigning the lowest schedule until we are certain it is too toxic, at which point the trial may start again using a lower dose of drug. When escalating, the treatment schedule cannot skip an untried dose but there will be no restriction on treatment schedule de-escalation. Each escalation decision will be made by the TMG based on the recommendation from the TiTE-CRM model and the accumulated experience of the

recommended schedule. If the TMG is unable to reach a decision or a stopping rule has been met the Safety Review Committee (SRC) will meet.

The trial consists of three stages A1, A2 and B which are described in the following sections. Stages A1 and A2 will run concurrently and will inform the starting dose of M6620 (Berzosertib) for Stage B.

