3.1.1 General description of the TiTE-CRM design

The TiTE-CRM method is a modified version of the CRM that accounts for late-onset toxicities. It uses all current information when deciding which dose to give the next patient and it is not necessary for a patient to complete the full observation period before consenting the next patient. This results in a better estimation of the MTD and shorter study duration respectively and is particularly useful in trials involving radiotherapy where the toxicity follow-up phase is longer. We assume that:

- A maximum of N subjects are to be recruited
- A target toxicity level, TTL
- K doses d_1, \dots, d_K to be explored
- A DLT window of length T
- The maximum amount of dose of M6620 for the patient's allocated treatment schedule D
- A weight function, w , associated with T and D denoting a combination of the proportion of the DLT window that has been observed and proportion of the total M6620 they're to receive for each currently enrolled patient
- Prior estimates of DLTs at each dose, also called the skeleton, $\hat{\pi}_0 = \{\hat{\pi}_{01}, \dots, \hat{\pi}_{0K}\}$
- Dose toxicity curve (DTC), $g_k(\alpha) = d_k^{\exp \alpha}$
- Prior distribution for the parameter of the DTC, $\alpha \sim N(0, \sigma^2)$

A phase I dose escalation safety study combining the ATR inhibitor VX-970 with chemoradiotherapy in oesophageal cancer using time to event continual reassessment method (funded by CRUK and Merck)
 EudraCT Number: 2015-003965-27

At the start of the trial the information on the probability of DLT at each dose level is given by the prior estimates $\hat{\pi}_0$. These estimates are updated after every patient to give the posterior estimates.

Suppose there are J subjects currently enrolled, the available information is the set of doses $\{x_1, \dots, x_J\}$ administered to the J patients, the set of toxicity outcomes $\{y_1, \dots, y_J\}$ where $y_j = 0$ if no toxicity and $y_j = 1$ if toxicity, and the amount of time each patient has been observed $\{u_1, \dots, u_J\}$, where $0 \leq u_j \leq T$. The amount of M6620 given per dose schedule $\{v_1, \dots, v_J\}$, where $0 \leq v_j \leq D$.

The TiTE-CRM model uses a weighted likelihood function given by

$$L(\alpha) = \prod_{j=1}^J \left[g_{x_j}(\alpha) * w_j \right]^{y_j} \left[1 - g_{x_j}(\alpha) * w_j \right]^{1-y_j}$$

where

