$$w_j = \begin{cases} 1 & \text{if } y_j = 1 \\ \frac{1}{2} \left(\frac{u_j}{T} + \frac{v_j}{D} \right) & \text{if } y_j = 0 \end{cases}$$

[figure not shown]
and the posterior expected toxicity at each dose (posterior dose-toxicity curve) is given by

$$\hat{\pi}_k = E(g_k(\alpha)|y) = \int_{-\infty}^{\infty} g_k(\alpha) p(\alpha|y) d\alpha$$

The MTD is defined to be the dose x^* such that $\hat{\pi}_k = TTL$. As each new patient is enrolled, the current best guess at the MTD is calculated based on all data accrued so far, and is the dose suggested for the patient in agreement with the TMG.

In addition the trial may be stopped early if either the drug is found to be too toxic or we are confident in our estimate of the MTD. The flow of patients through a CRM trial is given in Figure 1.

Figure 1: Flow of patients through a CRM trial

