Stage A1 will pause for safety if, at any point in the trial, there is sufficient evidence to suggest that schedule 1 is too toxic. More specifically, we will consider schedule 1 to be too toxic if, given all the available data, there is a high probability that the DLT rate is greater than the target toxicity level of 0.25. If all 3 patients in the first cohort have DLTs then schedule 1 is too toxic and the trial will be re-started. At this point, three extra schedules will be introduced at 90mg/m² and varying dosing frequencies, namely (schedule -3, -2 and -1). Once the trial is restarted, the lowest schedule, schedule -3, will be explored first. There will then be 9 treatment schedules to explore (the original 6 plus the 3 dosing frequencies at the lower dose). If the first 3 patients recruited to schedule -3 experience DLTs then the trial will stop. If schedule 1 is found to be too toxic later in the trial when more than 3 patients have been recruited, a SRC meeting will be convened to decide whether the trial should be restarted using the lower dose of 90mg/m².

Stage A1 will stop for success when either a total of 10 patients have been assigned to a particular treatment schedule or 20 patients have been recruited, whichever occurs first. When 10 patients in Stage A1 have been assigned to a particular treatment schedule, recruitment will be paused until there are no more than three patients without full follow-up (either DLT or 6 weeks after the end of treatment), i.e. until there is full follow-up information on at least seven patients. If the MTD changes, recruitment may start again.

Based on simulations and assuming a patient will be recruited every 8 weeks, the average number of patients required for Stage A1 is 18, which we aim to recruit in 24 months.

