3.4 Summary of trial design for all stages

The table summarises the design features of the design for stages A1 and A2, and Figure 1 shows the flow of patients through the trial.

Table 1: Design features for all stages of the study

Assumptions	A1	A2	B**
Target toxicity level	0.25	0.30	
Maximum number of subjects	20	20	
Number of treatment schedules	6	4	
Stopping rules	10 on a schedule	6 on schedule 4	
Toxicity stopping rules	$P(\text{Toxicity at treatment schedule 1} > \text{TTL} \text{data}) > 0.95$		
Definition of MTD	Treatment schedule that is closest to but not above the TTL		
Dose escalation rules	No dose skipping when escalating, no restrictions on de-escalation		
Dose toxicity curve	Power curve with prior $N(0, 1.158^2)$		
DLT window	9 weeks	4 weeks	

A phase I dose escalation safety study combining the ATR inhibitor VX-970 with chemoradiotherapy in oesophageal cancer using time to event continual reassessment method (funded by CRUK and Merck)

EudraCT Number: 2015-003965-27

[figure not shown]
Number in first cohort*	3	3
Skeleton	0.12	0.17
	0.15	0.20
	0.18	0.25
	0.20	0.30
	0.22	
	0.25	

* This is the number assigned the first treatment schedule

** Design features for Stage B omitted for this version of the SAP.

A phase I dose escalation safety study combining the ATR inhibitor VX-970 with chemoradiotherapy in oesophageal cancer using time to event continual reassessment method (funded by CRUK and Merck)
 EudraCT Number: 2015-003965-27

Figure 2: Trial Flow Chart

A phase I dose escalation safety study combining the ATR inhibitor VX-970 with chemoradiotherapy in oesophageal cancer using time to event continual reassessment method (funded by CRUK and Merck)
EudraCT Number: 2015-003965-27

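### In Stage A1 the written allocation rule can recommend untried schedule 6 directly after the stage's first DLT, in the only patient on schedule 5

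*SAP*

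**What the plan says.** SAP 3.2 gives the next patient the schedule with the estimated DLT rate nearest the target from below. The only restriction on going up is that "the treatment schedule can only increment by one level if escalating to an untried schedule". Protocol section 2 says the same: "When escalating, the treatment schedule cannot skip an untried dose but there will be no restriction on treatment schedule de-escalation". Table 1 in SAP 3.4 lists the escalation rules as "No dose skipping when escalating, no restrictions on de-escalation". None of these places says what happens to escalation directly after a DLT, or asks for a second patient on a schedule before the next step.

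The toxicity stop (SAP 3.3 and Table 1) tests only the lowest schedule: it acts when the probability that schedule 1 exceeds the target is above 0.95.

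The model's choice is a recommendation. Under SAP 3.2 the TMG may confirm it, replace it, or refer the decision to the Safety Review Committee. SAP 3.2 leaves the full detail of dose decisions to a Protocol Decision Point Plan, which is not among the documents. Its short account of that plan mentions no restriction after a DLT.

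**The concern.** A dose-finding rule is called coherent if it never moves up on the strength of a DLT. The no-skip restriction can break this. It holds assignments below the schedule that the model already prefers, so a DLT can raise every estimate and still leave the next, untried schedule under the target. The written rule then steps up although the one patient observed on the schedule below had a DLT.

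At stake is exposure of a patient to an untried schedule in the first combination of M6620 with radiotherapy (Protocol 1.4). There is also a question of description. If the committee would always reject such a step, the simulated operating characteristics do not describe the design that will be run.

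**Working it through.** **Inputs**

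- Target: "target toxicity level of 0.25" (SAP 3.1.1, Stage A1).
- Model: the "Dose toxicity curve (DTC" entry in the SAP's general description gives p_k(α) = s_k^exp(α). Table 1 has "Power curve with prior" N(0, 1.158²) for α.
- Skeleton s for A1 (first column of Table 1): 0.12, 0.15, 0.18, 0.20, 0.22, 0.25.
- Estimate: "the posterior expected toxicity at each dose (posterior dose-toxicity curve", that is, the posterior mean of p_k.
- Weight: 1 for a patient with a DLT; otherwise ½(u/T + v/D), with T = 9 weeks, u the time observed, v the M6620 received and D the M6620 planned.
- Spacing: 8 weeks is assumed for the simulations (SAP 3.1.1, Stage A1); the minimum gap is 4 weeks, which the TMG may shorten (Protocol 4.4).

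**The plan's own figure.** SAP 3.6 gives an average A1 sample size of 18 (10, 20). The true rates behind it are not in the documents. Taking truth equal to the skeleton as an assumption, 600 simulated trials gave a mean of 17.2, a median of 18 and a range of (10, 20). Five other assumed truths gave means of 16.7 to 19.4. The coded rule therefore behaves like the plan's.

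**The path at full follow-up**

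1. Three patients on schedule 1 and one each on schedules 2, 3 and 4, all DLT-free. The posterior mean at schedule 6 is 0.087. The model already prefers schedule 6; only no-skipping holds the next patient at schedule 5.
2. The schedule 5 patient has a DLT (1 DLT in 7 patients). The likelihood is (1 − p₁)³(1 − p₂)(1 − p₃)(1 − p₄)p₅. Integrating over the prior gives:

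| Schedule | 1 | 2 | 3 | 4 | 5 | 6 |
|---|---|---|---|---|---|---|
| Posterior mean | 0.130 | 0.156 | 0.182 | 0.199 | 0.216 | 0.242 |

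3. All six are below 0.25, so the rule selects schedule 6. The posterior probability that the schedule 6 rate exceeds 0.25 is 0.43. For schedule 1 it is 0.14, far below the 0.95 needed to stop.

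**Partial follow-up.** At 4-week spacing, with the decision 1 week after the schedule 5 patient starts, the schedule 4 patient has 5 weeks observed and all the planned M6620, so the weight is ½(5/9 + 1) = 0.78. Earlier patients have weight 1.

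| Gap | Decision after schedule 5 start | Mean at schedule 6 | Selected |
|---|---|---|---|
| 8 weeks | 1 to 8 weeks | 0.242 | 6 |
| 4 weeks | 1 to 4 weeks | 0.250 (0.2498 unrounded) to 0.244 | 6 |
| 3 weeks | 1, 2 weeks | 0.256, 0.252 | 5 |
| 3 weeks | 3 weeks | 0.248 | 6 |
| 2 weeks | 1, 2 weeks | 0.266, 0.260 | 5 |

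**How special the path is.** At full weights, 36 paths end with a DLT in the only schedule 5 patient. One, the path above, leads to schedule 6. The other 35 contain an earlier DLT and lead to schedule 3 (28) or schedule 2 (7). When the stage's first DLT falls on the only patient on schedule 2, 3 or 4, the model picks schedule 1, 2 or 4 respectively.

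**How often.** At full weights the probability is (1 − q₁)³(1 − q₂)(1 − q₃)(1 − q₄)q₅ for true rates q.

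- Truth = skeleton: 0.88³ × 0.85 × 0.82 × 0.80 × 0.22 = 0.084.
- Assumed 0.05, 0.08, 0.12, 0.18, 0.25, 0.40: 0.142.
- Assumed 0.10, 0.15, 0.20, 0.25, 0.35, 0.45: 0.130.

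Simulations under several assumed truths gave roughly 7 to 14% of trials at 8-week accrual and 4 to 7% at 4-week gaps.

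**If the step is barred.** Schedule 5 (mean 0.216) is then the highest the model may recommend. If a second schedule 5 patient had a DLT, the schedule 5 mean would be 0.304 and the model would fall to schedule 2. If not, the schedule 6 mean would be 0.217 and schedule 6 would open.

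**The case against.** The case against making much of this is strong in several respects.

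- **It is one boundary case.** A reader might infer that the rule generally escalates on DLTs. It does not: an earlier DLT, or a first DLT lower down, sends the model down or keeps it where it is. The margin at schedule 6 is also thin.
- **Larger frequencies count something else.** Counting every escalation made while all patients on the highest tried schedule had had a DLT gives about 15 to 30% of trials at 8-week accrual. That includes steps taken later, after further patients on lower schedules. In one split, 7 to 11% of trials had only such delayed steps. Those steps are not escalation directly after a DLT.
- **People decide.** A reader might infer that the next patient is sent to schedule 6 automatically. Protocol section 2 and SAP 3.2 give the decision to the TMG, which works to a charter (Protocol 19.1). The Safety Review Committee can review DLTs and dose decisions (Protocol 19.2). Four sensitivity analyses, one assuming the worst for patients still under observation, go to each dose decision meeting (SAP 7.4).
- **Unseen documents.** The Decision Point Plan may contain the restriction. The simulation results are in a separate appendix (SAP 1.2).
- **The added exposure is limited.** Schedule 6 adds one infusion, on day 19, to schedule 5 at the same dose (Protocol Table 8.1).

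All of this limits the size of the point. It does not remove it: the committee's safeguard is discretionary, and the written rule gives it a recommendation that it may well want to reject in a foreseeable case.

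**Conclusion.** The point holds in a limited form. When the stage's first DLT is in the only schedule 5 patient and earlier patients are at or near full follow-up, as at 8-week accrual or the 4-week minimum gap, the written rule recommends untried schedule 6. Nothing else written in the algorithm prevents this.

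The worked path rests only on Table 1 and the SAP's formulas. The frequencies rest on assumed true DLT rates, because those used by the sponsor are not given.

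A must-fix grade is not supported. A stricter block, barring an untried schedule whenever the observed DLT proportion on the highest tried schedule exceeds 0.25, left mean correct selection about the same in one set of simulations (28.3% against 28.7%), with 0.1 to 0.6 fewer patients per trial above target at 8-week accrual. Another set found 0.05 to 0.13 fewer expected DLTs per trial at 8 weeks, and at 4 weeks changes from +0.03 to −0.12. These average effects are small and not clearly beyond simulation noise. The reason to act is to protect the individual patient on this path, at low cost.

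**What to change.** Add one sentence to SAP 3.2, with matching entries in Table 1 and Protocol section 2: the model's recommendation may not move to an untried schedule directly after a DLT in the most recent patient on the highest tried schedule. If the Decision Point Plan already has such a rule, state it in these places. Then rerun the simulations with the restriction, so that the reported operating characteristics match the rule in use.

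This limits the algorithm only; the choice of schedule stays with the TMG. The stricter proportion-based block is not needed. With 1/1, 1/2 and 1/3 all above 0.25, it would require at least four patients on a schedule after one DLT before any step up.

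The cost is one sentence in each document, one line of code and a rerun. The downside is that an occasional extra patient stays at the current schedule before a step up.

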3.3 Stopping rules for toxicity

The same stopping rule for safety applies to all 3 stages of the study: each stage will stop for safety if, at any point in the stage, there is sufficient evidence to suggest that the lowest treatment schedule is too toxic. Specifically, within a particular stage, the lowest schedule will be considered too toxic if, given all the available data, there is a high probability that the DLT rate is greater than the target toxicity level for that stage, i.e. if $P(\text{Toxicity at treatment lowest schedule} > \text{TTL} | \text{data}) > 0.95$.

3.4 Summary of trial design for all stages

The table summarises the design features of the design for stages A1 and A2, and Figure 1 shows the flow of patients through the trial.

Table 1: Design features for all stages of the study

Assumptions	A1	A2	B**
Target toxicity level	0.25	0.30	
Maximum number of subjects	20	20	
Number of treatment schedules	6	4	
Stopping rules	10 on a schedule	6 on schedule 4	
Toxicity stopping rules	$P(\text{Toxicity at treatment schedule 1} > \text{TTL} \text{data}) > 0.95$		
Definition of MTD	Treatment schedule that is closest to but not above the TTL		
Dose escalation rules	No dose skipping when escalating, no restrictions on de-escalation		
Dose toxicity curve	Power curve with prior $N(0, 1.158^2)$		
DLT window	9 weeks	4 weeks	

A phase I dose escalation safety study combining the ATR inhibitor VX-970 with chemoradiotherapy in oesophageal cancer using time to event continual reassessment method (funded by CRUK and Merck)

EudraCT Number: 2015-003965-27

[figure not shown]
Number in first cohort*	3	3
Skeleton	0.12	0.17
	0.15	0.20
	0.18	0.25
	0.20	0.30
	0.22	
	0.25	

* This is the number assigned the first treatment schedule

** Design features for Stage B omitted for this version of the SAP.

A phase I dose escalation safety study combining the ATR inhibitor VX-970 with chemoradiotherapy in oesophageal cancer using time to event continual reassessment method (funded by CRUK and Merck)
 EudraCT Number: 2015-003965-27

Figure 2: Trial Flow Chart

A phase I dose escalation safety study combining the ATR inhibitor VX-970 with chemoradiotherapy in oesophageal cancer using time to event continual reassessment method (funded by CRUK and Merck)
EudraCT Number: 2015-003965-27

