This phase I study will test the combination of a novel ATR inhibitor (M6620 (Berzosertib)) with chemoradiotherapy in oesophageal cancer. In the first two cohorts (Stage A1 and A2), we will investigate the safety of combining M6620 (Berzosertib) separately with [1] palliative radiotherapy (RT) for oesophageal cancer (Stage A1) and [2] with cisplatin/capecitabine chemotherapy in patients with advanced inoperable and metastatic solid tumours (Stage A2). In Stage A1, M6620 (Berzosertib) will be given in combination with high dose palliative RT treatment, aiming to deliver M6620 (Berzosertib) twice weekly during RT escalating to a dose of 240mg/m². A palliative chemotherapy cohort (Stage A2) will open to recruitment simultaneously where M6620 (Berzosertib) will be given in combination with cisplatin/capecitabine chemotherapy, aiming to deliver M6620 (Berzosertib) twice weekly escalating to a dose of 140mg/m² twice weekly. When adequate toxicity and follow-up information to suggest the combinations are tolerable has accumulated, the ATR inhibitor will be tested in the definitive setting (Stage B) in combination with cisplatin/capecitabine and radical RT to identify the Maximum Tolerated Dose (MTD). The MTD found in this study will be taken forward in future phase II studies.

In the palliative setting, we aim to find the schedule associated with no more than 25% Dose Limiting Toxicities (DLTs) in stage A1 on the basis that palliative oesophageal radiotherapy causes approximately 20% grade 3 and 4 toxicity and 30% Dose Limiting Toxicities (DLTs) in stage A2 are derived from capecitabine/cisplatin used in the radical setting (SCOPE1 study [12]).

In the radical setting, we aim to find the schedule associated with no more than 45% DLTs on the basis that conventional oesophageal chemoradiation causes a grade 3 and 4 toxic event rate of 28% haematological toxicity and 63% non-haematological toxicity of which 34% is gastrointestinal as reported in the standard arm of SCOPE1 study (12). Comparable toxicity rates were described in the standard arm of the PRODIGE5/ACCORD17 study (13): grade 3 and 4 neutropenia 29% and grade 3 and 4 dysphagia and oesophagitis 33%.

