2.2.1. Stage A2 stopping rules

Stage A2 will stop for safety if, at any point in the trial, there is sufficient evidence to suggest that schedule 1 is too toxic. More specifically, we will consider schedule 1 to be too toxic if, given all the available data, there is a high probability that the DLT rate is greater than the target toxicity level of 0.3. If the first three patients recruited to Stage A2 have DLTs at treatment schedule 1, then the starting schedule (treatment schedule 1) will be deemed too toxic and the trial will stop.

The trial will stop for success when either six patients have been assigned to the fourth treatment schedule (140 mg/m² of M6620 (Berzosertib) twice weekly) or 20 patients in total have been recruited, whichever occurs first. When six patients in Stage A2 have been assigned to the fourth treatment schedule, recruitment to Stage A2 will be paused until there is full DLT follow-up information on at least five patients. If the MTD has changed, recruitment to Stage A2 may start again.

Based on simulations and assuming a patient will be recruited every 3 weeks, the average number of patients required for Stage A2 is 16, which we aim to recruit in 12 months.

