3.1.2 Stage A2

The aim is to find the M6620 treatment schedule when combined with palliative combination chemotherapy (Cisplatin and Capecitabine) that is associated with no more than a 30% dose limiting toxicity rate. Four treatment schedules are proposed. Each schedule comprises a specific combination of dose and dosing frequency. There are two possible M6620 doses and two dosing frequencies (see section 4.2.1). Chemotherapy dose remains consistent across all treatment schedules. For the prior estimates of DLT at each treatment schedule see the skeleton in Table 1.

The treatment involves six cycles of chemotherapy with three weekly Cisplatin and Capecitabine and M6620 at a pre-determined frequency dependent on the treatment schedule allocated to the individual patient. The follow-up of a further 8 weeks provides a total observation window of 26 weeks. DLT assessments will be carried out during the first 4 weeks of treatment. The MTD will be determined during this period using the TiTE-CRM. An initial cohort of three patients will receive the starting schedule (lowest dosing frequency) at the starting dose. The fourth patient will not be recruited until all three patients have been followed for a minimum of 4 weeks from the start of chemotherapy or until the occurrence of a DLT.

From the fourth patient, all eligible patients will be continuously recruited and the TiTE-CRM will be used to assign their treatment schedule. To ensure enough information is accumulated to inform the assignment of the treatment schedule to the subsequent patient, recruitment will be managed by allocating treatment slots (see Protocol section 4.4 for further details).

Stage A2 stopping rules

Stage A2 will stop for safety if, at any point in the trial, there is sufficient evidence to suggest that schedule 1 is too toxic. More specifically, we will consider schedule 1 to be too toxic if, given all the available data, there is a high probability that the DLT rate is greater than the target toxicity level of 0.3. If the first three patients recruited to Stage A2 have DLTs at treatment schedule 1, then the starting schedule (treatment schedule 1) will be deemed too toxic and the trial will stop.

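### The Stage A1 and A2 MTD is defined by the model estimate alone, so a schedule given to very few patients, or to none, can be declared

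*SAP*

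**What the plan says.** - **Definition.** SAP 3.4, Table 1 gives the MTD for A1 and A2 as "Treatment schedule that is closest to but not above the TTL". SAP 3.1.1 (general description) and 7.2.1 present posterior estimates with credible intervals. Neither mentions a number treated.
- **Assignment.** SAP 3.2 forbids skipping an untried schedule and lets the TMG confirm or overrule the model, taking account of experience on the recommended schedule. These rules concern the next patient.
- **Success stops.** A1 stops at 10 patients on any one schedule or 20 in total. For A2, Protocol 2.2.1 says "The trial will stop for success when either six patients have been assigned to the fourth treatment schedule", or at 20 in total. If the MTD changes after the follow-up pause, recruitment may restart. That is optional and is not described as going past 20.
- **Use.** Protocol section 3 labels each stage's schedule the recommended phase II dose. Protocol 1.1 says Stage B is run to identify the MTD, then adds: "The MTD found in this study will be taken forward in future phase II studies".

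**The concern.** The no-skipping rule limits who is given what. It does not limit what is named at the end. The last patients' DLT-free follow-up enters the model only after the last assignment, so the final estimates can fall and move the declared schedule up to one with little or no direct experience. The success rules do not prevent this: neither ties its count to the schedule finally declared, and the 20-patient cap bypasses both. The primary endpoint of each stage could then rest on extrapolation through a one-parameter curve.

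**Working it through.** **Inputs.** From SAP 3.4: targets 0.25 (A1) and 0.30 (A2); skeletons 0.12/0.15/0.18/0.20/0.22/0.25 and 0.17/0.20/0.25/0.30; power curve with a N(0, 1.158²) prior; DLT windows of 9 and 4 weeks; first cohort of 3; cap of 20; safety stop at posterior probability 0.95. From SAP 3.1: one patient per 8 weeks (A1) and per 3 weeks (A2). Not in the documents, so assumed: the true DLT curves, DLT times, even accrual and M6620 compliance. Runs used 800 to 3,000 trials per curve.

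**Reproducing the plan's figure.** With the skeleton as truth and follow-up-only weights, mean sample size is 17.3 to 17.8 (range 10 to 20) in A1, against the stated 18 (10, 20). In A2 it is 15.9 to 16.3 (11 to 20), against 16 (11, 20).

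**Paths inside the written rules, final fit with full follow-up.**
- A2, DLTs in patients 3, 5, 6 and 7: counts 16/4/0/0, N = 20, posterior means 0.208/0.239/0.289/0.338. The highest at or below 0.30 is schedule 3, with **no** patients.
- A1, DLTs in patients 4, 7 and 11: counts 8/7/2/2/1/0, N = 20. Schedule 5 is at 0.229 and schedule 6 at 0.258, so schedule 5 is declared, with **one** patient.
- A2, DLTs in patients 8, 10 and 11: counts 3/1/1/6, stopped for success at N = 11, posterior means 0.200/0.229/0.276/0.323. Schedule 3 is declared, with **one** patient unless the optional restart is used.

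**Frequency, A1** (trials that declare an MTD). With resumption: fewer than 3 patients in 3.5 to 25%, none in 0.2 to 0.8%. Without: 11 to 26% and 2.6 to 8.4%.

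**Frequency, A2.** The result depends on the weight w = ½(u/T + v/D), described in SAP 3.1.1 as "denoting a combination of the proportion of the DLT window that has been observed and proportion of the total M6620". D is the maximum M6620 for the allocated schedule, and SAP Table 3 runs those schedules for 18 weeks. Read literally, a DLT-free patient at week 4 has w = ½(4/4 + 4/18) = 0.61. One who stops after four cycles ends at ½(1 + 12/18) = 0.83.

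| A2 assumption (recruitment resumes) | Fewer than 3 | None |
|---|---|---|
| Follow-up-only weights, six curves | 2.5-8.7% | 0.4-2.8% |
| New weights or plug-in estimate | 1.4-10% | not summarised separately |
| D over 4 weeks or follow-up-only weights, other curves | 7-11% | 2-3% |
| D over 18 weeks, mixed 6/12/18 weeks received | 10-14% | 3-5% |
| D over 18 weeks, all stop after 4 cycles | 12-14% | 4-5% |
| D over 18 weeks, final weights 1 | 14-21% | 6-9% |

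Without resumption, follow-up-only weights give 5.5 to 16% and 0.2 to 3.2%.

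**How little 2 patients show directly.** With no DLTs in n patients the exact one-sided 95% upper limit is 1 - 0.05^(1/n): 78% for n = 2, 39% for n = 6, 26% for n = 10.

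**Effect of a minimum of 3 on over-target declarations.**
- A1: 19% to 13% and 29% to 23%; under steep curves, from 32-37% to 24-28%.
- A2, D over 18 weeks and final weights 1: 41% to 34% and 30% to 24%.
- A2, four cycles only: 25% to 22% and 16% to 13%.
- A2, D over 4 weeks or follow-up-only weights: 2 to 4 points lower.

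**The case against.** **The CRM borrows across schedules.** The count on one schedule is not the information behind its estimate. This stands: what is thin is direct experience, not the whole fit.

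**Thin declarations are a minority.** The median number on the declared schedule was 4 to 10 in A1 and 6 to 14 in A2 with follow-up-only weights. This stands too.

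**A reader might infer that the phase II schedule itself will rest on 0 to 2 patients.** The documents do not support that. They place identification of the MTD for phase II in Stage B, which has its own three schedules and 15 to 25 patients. The label of recommended phase II dose on A1 and A2 keeps the point relevant, but no more.

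**A reader might take the high A2 figures as the result.** They need every DLT-free patient to reach weight 1. No passage sets final weights to 1, cycles 5 and 6 depend on CT and the investigator's discretion (Protocol, Stage A2 schedule of events), and Protocol 9.3.1 allows dose reductions after week 4.

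**A reader might infer that thin declarations are always the over-toxic ones.** Under steep A1 curves they exceeded target in 52 to 78% of cases, against 25 to 27% otherwise. In one of two A2 curves they did so less often.

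**Safeguards exist.** The TMG can overrule the model, the Safety Review Committee reviews recommended-dose decisions (Protocol 19.2), and Protocol 18.5 tabulates DLTs by schedule. None sets a rule for the declaration. The simulation appendix and Decision Point Plan that the SAP cites were not available.

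**Conclusion.** The gap is real for A1 and A2, and filling it is a cheap improvement. Nothing in either document requires that the declared schedule was given to a minimum number of patients, or to any, and 0, 1 and 2 are all reachable under the written rules. The frequencies above are ranges over assumed curves, weights and compliance. The A2 figures in particular should be quoted as a range, not at their upper end. Barring an untried schedule costs almost nothing. The minimum of 3 is a trade-off, because restricting the candidates can only move the choice downward. The same gap holds in Stage B, but its frequency cannot be computed because the SAP omits that stage's design features.

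**What to change.** In SAP Table 1 and 7.2.1, define the declared MTD as the highest schedule with posterior mean at or below the target among schedules actually given. Preferably restrict this to schedules with at least 3 patients who had a DLT or completed the DLT window; 3 is the plan's own first-cohort size. Report the number treated and the number of DLTs on the declared schedule beside its credible interval. Set the Stage B rule in the same way when its SAP section is written.

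In the first A2 path above, either version names schedule 2 (4 patients, 0.239). In the A1 path, the tried-only rule keeps schedule 5, while the minimum of 3 names schedule 2 (7 patients, 0.162).

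**Cost.** SAP wording and no extra patients. The downside of the minimum of 3 is a change in correct selection of about +2 to -6 points. When the top schedule is right, it is named less often (A2 56% to 50%, A1 78% to 76%). The loss is not confined to that case: with A2 truth 0.20/0.30/0.45/0.55, schedule 1 rises from 35% to 44% and the correct schedule 2 falls from 33% to 30%. If the sponsor would rather recruit until 3 are reached, the mean addition is 0.3 to 0.6 patients in A1 and 0.1 to 0.3 in A2. The total would then pass 20 in 2 to 18% of A1 trials and 2 to 7% of A2 trials, so the cap would need a stated exception.
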